13.5.4 Trial Feasibility Parameters

Trial feasibility parameters will be summarized using descriptive statistics. Formal hypothesis testing will not be conducted; rather, observed quantities will be compared to performance benchmarks based on typical RTOG trials. Some specific expectations are as follows:

- Credentialing: 100% credentialing completed and documented before patient enrollment;
- Eligibility: Among screened and enrolled patients, 95% retain eligibility status after central review by RTOG Headquarters staff;
- Baseline forms: Completed and provided within 30 days of registration;
- Follow-up forms and delinquency: Follow-up loss < 3% where follow-up loss is defined as the proportion of patients unavailable to be evaluated for the primary endpoint due to loss of contact, follow-up assessment provided within 60 days of evaluation time point.

13.6 Data Monitoring Committee, Interim Analyses, and Stopping Criteria

An independent Data Monitoring Committee will be constituted to oversee this trial. Accrual, other study conduct parameters, and adverse events will be reviewed at semi-annual meetings of this committee.

One formal analysis for futility with respect to demonstrating noninferiority will be performed after completion of enrollment and follow up to 1 year, including only those patients who have reached the 2-year follow-up time point. Early reporting will be considered if the estimated 2-year local-regional control rate in the SBRT arm (Arm 2) is less than 60% (in which case the exact upper one-sided 95% confidence bound would fall below 75%, the threshold noninferiority value for this trial), and if this rate is more than 15% lower than the observed rate in the RODS arm (Arm 1).

Results for dissemination will be developed, and a manuscript drafted for review, approval, and submission. After manuscript acceptance, patient follow up will be discontinued and the trial terminated. It is anticipated that termination will occur approximately 5.5 years from initiation of patient entry. This time-frame may be extended depending on factors such as the observed accrual and event rates, in which case a new trial termination date will be established.

REFERENCES

1. Jemal, A., et al., *Cancer statistics, 2009*. CA Cancer J Clin, 2009. **59**(4): p. 225-49.
2. Yang, B.H., et al., *Cancer burden and trends in the Asian Pacific Rim region*. Asian Pac J Cancer Prev, 2004. **5**(2): p. 96-117.
3. Pisani, P., D.M. Parkin, and J. Ferlay, *Estimates of the worldwide mortality from eighteen major cancers in 1985. Implications for prevention and projections of future burden*. Int J Cancer, 1993. **55**(6): p. 891-903.
4. Rami-Porta, R., et al., *The IASLC Lung Cancer Staging Project: proposals for the revision of the T descriptors in the forthcoming (seventh) edition of the TNM classification for lung cancer*. J Thorac Oncol, 2007. **2**(7): p. 593-602.
5. Hsu, C.P., et al., *Surgical-pathologic factors affect long-term outcomes in stage IB (pT2 N0 M0) non-small cell lung cancer: a heterogeneous disease*. J Thorac Cardiovasc Surg, 2009. **138**(2): p. 426-33.
6. Iwasaki, A., et al., *Results of video-assisted thoracic surgery for stage I/II non-small cell lung cancer*. Eur J Cardiothorac Surg, 2004. **26**(1): p. 158-64.

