13.3 Sample Size

This randomized phase II trial will compare SBRT and RODS among patients with T1N0M0 NSCLC.

The trial is designed to determine whether there is a 15% or smaller absolute decrement in local-regional tumor control at 2 years for SBRT relative to RODS. Specifically, we assume that patients treated with RODS will have 90% of 2 year local regional control, and aim to demonstrate that those with SBRT would have no greater than 15% lower local-regional control largely due to lack of nodal dissection, or 75% local-regional control. The rationale for permitting up to 15% lower 2-year local tumor control for the SBRT arm is that SBRT is expected to have equivalent survival as such local failure would be effectively salvaged by surgery, radiation, chemotherapy or combined trimodality therapy [252]. Additionally, we expect the patients treated with SBRT would

have a better quality of life and more favorable toxicity profiles (less severe treatment complications such as inter-operative death). The null hypothesis is that SBRT has a > 15% lower local-regional control rate, and the alternative is that the difference is 15% or less. To ensure probability of 0.80 for correctly concluding that the difference is 15% or less (that is, when this is the true state) and probability 0.20 of falsely concluding that the difference exceeds 15%, 36 patients per treatment arm is required, a total of 72 patients. To account for ineligible patients and attrition of the cohort during the 24-month follow up, a 5% inflation of the sample size is applied, leading to a **total of 76 patients**. With 24 months of accrual and a minimum follow-up of 24 months, the trial will be completed.

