13.4 Accrual

Five institutions will participate in this trial. It is estimated that 100 patients in each participating center will undergo a complete resection for stage I NSCLC each year. Of these patients, 5-10% are expected to consent to enroll on this trial. Thus, we anticipate that enrollment will be completed in 24 months. We plan to report primary results at a maximum of 2 years after the last patient has been enrolled (i.e. when all patients have accumulated either 2 years of follow up or a primary endpoint failure event).

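### The 60% futility cut-off in Section 13.6 does not guarantee the stated upper bound below 75% at the interim size the schedule implies; the property is assured only from 28 evaluable patients per arm

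*Combined protocol and SAP*

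**What the plan says.** Section 13.6 plans one formal futility analysis, timed "after completion of enrollment and follow up to 1 year" and "including only those patients who have reached the 2-year follow-up time point". Early reporting is to be considered when two conditions both hold. The first is that the "estimated 2-year local-regional control rate in the SBRT arm (Arm 2) is less than 60"%. The second is that this rate is also more than 15 points below the rate observed with RODS. A parenthesis supports the first condition: "in which case the exact upper one-sided 95% confidence bound would fall below 75%, the threshold noninferiority value for this trial".

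The number of patients expected at this look is not given. What can be inferred comes from two other sections. Section 13.3 requires 36 evaluable patients per arm (72 in all, inflated by 5% to 76) and sets the timetable: "With 24 months of accrual and a minimum follow-up of 24 months, the trial will be completed". Section 13.4 counts on five centers with 100 resections a year each, of whom "5-10% are expected to consent to enroll on this trial".

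**The concern.** The parenthesis names the method (exact), the side, the level and the target value, and it claims the result for any SBRT estimate below 60%. Whether that is true depends only on how many SBRT patients are evaluable. It is true for a complete arm, but the look is not taken on a complete arm: patients enrolled in the last year of accrual have not reached 2 years and are left out.

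This is the trial's only formal futility rule. A monitoring committee reading the parenthesis would take a triggered rule to mean that the SBRT data exclude 75% at the one-sided 95% level. At the decision boundary that may not be so.

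**Working it through.** **Inputs.** Cut-off 60%, exact one-sided 95% bound, target 75% and timing of the look: Section 13.6. Sample size 36 per arm evaluable and 76 enrolled, 24 months of accrual, RODS control 90%, margin 15 points: Section 13.3. Accrual of 25 to 50 patients a year (5 × 100 × 5% to 5 × 100 × 10%): Section 13.4.

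**Formula.** For x controlled patients out of n, the exact (Clopper-Pearson) one-sided 95% upper bound is the 0.95 quantile of a Beta(x + 1, n − x) distribution. The claim is tested at the largest x with x/n strictly below 0.60, because that count gives the highest bound.

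**The plan's figure at full size.** 21/36 = 58.3% gives 72.3%, and 22/38 = 57.9% gives 71.5%. Both are below 75%, so the claim holds there.

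**Interim size (assumption: even accrual, equal arms, look exactly 12 months after the last entry).** Everyone except the last year's enrollees has reached 2 years, so n per arm = (76 − annual accrual)/2.
- 24 months of accrual: 38 a year, (76 − 38)/2 = 19; × 72/76 = 18 after the planned loss.
- 50 a year: (76 − 50)/2 = 13; × 72/76 = about 12.
- 25 a year: (76 − 25)/2 = 25.5; × 72/76 = about 24.

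**The claim at those sizes.**

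| n per arm | Highest count below 60% | Exact upper bound | Claim | Largest count with bound below 75% |
|---|---|---|---|---|
| 13 | 7 (53.8%) | 77.6% | fails | 6 |
| 18 | 10 (55.6%) | 75.6% | fails | 9 (bound 70.9%) |
| 19 | 11 (57.9%) | 77.0% | fails | 10 (bound 72.6%) |
| 20 | 11 (55.0%) | 74.1% | holds | 11 |
| 24 | 14 (58.3%) | 75.4% | fails | 13 |
| 25 | 14 (56.0%) | 73.0% | holds | 14 |
| 27 | 16 (59.3%) | 75.2% | fails | 15 |
| 28 | 16 (57.1%) | 73.1% | holds | 16 |

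Over every n, the claim fails from 12 to 19 and at 21, 22, 24 and 27. It holds at 20, 23, 25 and 26, and at each size from 28 to 38. At 18 and 19 only the one count shown fails. At 12 two counts fail: 7/12 (81.9%) and 6/12 (75.5%).

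To have 28 evaluable per arm one year after enrolment closes, with 38 per arm enrolled over A months, 38 × (A − 12)/A must equal 28, so A is about 46 months. With 36 per arm it is 54 months. At 25 patients a year, 76 patients take about 36 months.

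**How often the rule is met.** The probability that both conditions hold is the sum, over SBRT counts x up to the cut-off and RODS counts y with (y − x)/n > 0.15, of Bin(x; n, p_SBRT) × Bin(y; n, 0.90).

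| n per arm | True SBRT 75%: as written | True SBRT 75%: bound below 75% | True SBRT 60%: as written | True SBRT 60%: bound below 75% |
|---|---|---|---|---|
| 13 | 8.0% | 2.4% | 42% | 23% |
| 18 | 5.7% | 1.9% | 44% | 26% |
| 19 | 7.7% | 2.9% | 51% | 33% |
| 20 | 4.1% | 4.1% | 40% | 40% |
| 25 | 3.0% | 3.0% | 41% | 41% |

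The boundary count matters: with true SBRT control of 75%, 10/18 accounts for (5.7 − 1.9)/5.7, about two thirds, of all occasions on which the rule is met at 18 per arm.

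**The case against.** The best case for leaving the rule alone has four parts.

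- **The interim number is an inference.** One more evaluable SBRT patient (20 instead of 19) makes the claim true. This is right as far as it goes. But the parenthesis carries no sample-size condition, and the claim fails at 11 of the 14 sizes from 12 to 25.
- **The parenthesis is explanation, not rule.** The two operative conditions are unambiguous at any n, early reporting is only considered, enrolment is already closed, and the final analysis is untouched. All of this stands and limits the consequence. The RODS condition does not repair the claim, however: 10/18 (55.6%) against an observed RODS rate near 90% meets both conditions with a bound above 75%.
- **The design tolerates more error than this.** Section 13.3 accepts a probability of 0.20 of wrongly concluding that the deficit exceeds 15 points, and 5.7% to 7.7% is well inside that. At an 80% level the upper bounds are 67.5% (10/18) and 69.3% (11/19). So 60% is not a lax cut-off by the trial's own standard. What fails is the stated 95% property.
- **Another interval would pass.** The Wilson one-sided 95% bound is 72.8% for 10/18 and 74.4% for 11/19. The plan specifies the exact bound, so this does not rescue the text.

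**Conclusion.** The justification for the 60% cut-off is wrong as written. It holds at full arm size but is not guaranteed at the size the schedule implies, where the highest qualifying results exceed 75% by 0.6 points (18 per arm) to 2.0 points (19 per arm). With true control of 75% on SBRT and 90% on RODS, the rule is met about 2.7 to 3 times as often at those sizes as a cut-off with the claimed property would be (7.7/2.9 and 5.7/1.9).

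The bounds themselves are exact arithmetic. The interim size rests on even accrual, equal arms and a look 12 months after the last entry. Under the slowest accrual in Section 13.4 the claim is true at 25 per arm and fails narrowly at 24. The point should be corrected, but its effect on the trial is modest because the rule is non-binding and applies after enrolment closes.

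**What to change.** State in Section 13.6 the number per arm expected at the futility look and the accrual assumption behind it. Then do one of the following.

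1. **Define the first condition by the bound.** Early reporting comes into consideration when the exact one-sided 95% upper bound for SBRT 2-year control, computed on the patients then evaluable, lies below 75%. That means at most 6/13, 9/18, 10/19, 11/20 or 14/25. Keep the comparison with RODS. The cost is sensitivity: with true SBRT control of 60% and RODS 90%, the chance of meeting the rule falls from 51% to 33% at 19 per arm, from 44% to 26% at 18 and from 42% to 23% at 13. It is unchanged at 20 and 25.
2. **Keep 60% and correct the parenthesis.** Say that the bound is assured to fall below 75% only with about 28 or more evaluable patients in the SBRT arm. The rule then behaves exactly as it does now.

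Either way the change is to the wording of the analysis plan and the monitoring committee's instructions only. The second option is enough to remove the error. The first suits a sponsor who wants a triggered rule to mean that 75% has been excluded.

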APPENDIX I (6-AUG-2018)

The consent form is a separate document from the protocol and has been reviewed by the new RTOG Foundation-contracted IRB vendor, Advarra.

APPENDIX II: STUDY PARAMETER TABLE: *See section 11.1 for details and exceptions

Assessments	Within 6 wks prior to registration, unless otherwise noted	Arm 1				Arm 2				Both Arms
		Prior to surgery in clinic OR Pre-Op OR prior to surg.remove of tumor	Intra-Op after surgical removal of tumor	Prior to dis-charge	4-6 wks Post-Op	Prior to 1st fraction of SBRT	After 3 rd fraction of SBRT	After all SBRT (the last day)	4-6 weeks after end of SBRT	
History & Physical	X				X				X	X
Thoracic Surgeon evaluation	X									
Document weight	X				X				X	X
Performance Score	X				X				X	X
PFTs (with DLCO)	X									X*
FDG-PET/CT scan	Within 4 wks				X					At 3, 12, 24 mos.
CT of chest/upper abdomen, with contrast	Within 4 wks				X					Chest CT with contrast at 3,6,9, 12, 18, 24, 36 mos.
EBUS	Within 4 wks prior to treatment									
Adverse event assessment					X			X	X	X
Pregnancy test, if applicable	Within 72 hrs.									
†Blood for research		X	X	X	X	X	X	X	X	
†Tissue for banking	For Both Arms: prior to treatment									

†For patients who consent to participate in the specimen banking component of the study; see Appendix I.

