Surgical treatment is invasive and associated with significant mortality and morbidity [47-52]. The reported mortality rates are 7.2% in China (for T4 tumors) [53], 2.4-4.9% in Europe [49, 54], and 4.5% in the U.S. within 30 days post-lobectomy. In 128 patients with screen-detected peripheral lung nodules who underwent a video-assisted thoracic surgical (VATS) lobectomy, grade 3 or greater complications were seen in 7.4% (out of 95 patients) and the 30-day perioperative mortality was 2.7% [55]. Similarly, operative complications occurred in 27% of patients with screen-detected lung nodules who underwent a thoracotomy, and the corresponding operative mortality was 1.7% [56]. While morbidities may vary from report to report [48, 57-59], most of the studies reported mortality rates of 1-7% associated with surgical intervention (Table 1a).

1.2

Treatment Outcome of Stereotactic Body Radiation Therapy (SBRT)

SBRT is an emerging radiation (RT) technique that targets very high-dose RT precisely to a tumor while minimizing dose to adjacent normal tissue. SBRT derived from stereotactic radiosurgery, which was first developed in the late 1950's for the treatment of intracranial lesions. Stereotactic radiosurgery, normally with high-dose RT delivered in 1 fraction under stereotactic targeting, provides equivalent treatment results as a craniotomy with surgical resection. Recent advances in RT planning, such as 3DCRT and intensity modulated radiation therapy (IMRT), motion control, and on board image (OBI), and image guided radiation therapy (IGRT) during treatment delivery in the last decade have led to the application of this technique to extracranial sites. While stereotactic RT refers to high-dose RT in a fractionated fashion to any organ sites (intra- or extracranial sites), SBRT has been adopted for stereotactic RT to extracranial body sites including lung. The U.S. National Cancer Institute defines SBRT as "a type of external radiation therapy that uses special equipment to position a patient and precisely deliver radiation to tumors in the body (except the brain). The total dose of radiation is divided into smaller doses given over several days. This type of radiation therapy helps spare normal tissue."

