2.2 Secondary Objectives

2.2.1 To qualitatively and quantitatively assess feasibility of this joint RTOG-China clinical trial. Parameters to be assessed include satisfaction of pre-registration requirements (e.g. surgical and RTQA credentialing), patient accrual rate, patient eligibility rate, randomization conduct baseline forms completion and timeliness, follow-up forms completion/delinquency, and loss to follow-up rate;

2.2.2 To compare overall survival and disease-free survival between study arms;

2.2.3 To estimate and compare time to local-regional failure, time to distant metastases, and patterns of failure between study arms;

2.2.4 To compare treatment toxicities using the Common Terminology Criteria for Adverse Events (CTCAE, v. 4) between study arms; specific comparisons will include adverse events at 1, 3, 12, 24, and 36 months post-therapy;

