6.8.1 Adverse Events (AEs)

Definition of an AE: Any unfavorable and unintended sign (including an abnormal laboratory finding), symptom, or disease temporally associated with the use of a medical treatment or procedure regardless of whether it is considered related to the medical treatment or procedure (attribution of unrelated, unlikely, possible, probable, or definite).

AEs, as defined above, experienced by patients accrued to this protocol should be reported on the AE section of the appropriate case report form (see Section 12.1).

NOTE: If the event is a Serious Adverse Event (SAE) [see next section], further reporting will be required. Reporting AEs only fulfills Data Management reporting requirements.

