6.8.2 Serious Adverse Events (SAEs)

Definition of an SAE: Any serious adverse experience occurring during any part of protocol treatment and 30 days after whether or not related to the study drug that results in any of the following outcomes:

- Death;
- A life-threatening adverse drug experience;
- Inpatient hospitalization or prolongation of existing hospitalization;
- A persistent or significant disability/incapacity;
- A congenital anomaly/birth defect.

Important medical events that may not result in death, be life threatening, or require hospitalization may be considered an SAE, when, based upon medical judgment, they may jeopardize the patient and may require medical or surgical intervention to prevent one of the outcomes listed in the definition.

SAE reporting is safety related and separate and in addition to the Data Management reporting requirements as outlined in the previous AE reporting section.

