6.9 Serious Adverse Event (SAE) Reporting Requirements

It is the responsibility of the investigator to document all adverse events which occur during the study.

In addition to standard practice of recording AEs and SAEs on the case report form, this study will utilize an RTOG SAE Report Form for reporting of SAEs. The SAE Report Form, SAE Reporting Guidelines, and SAE Report Form Instructions are available on the RTOG web site, www.RTOG.org.

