6.9.1 Reporting SAEs

Any SAE that occurs during any part of protocol treatment and 30 days after whether or not related to the study treatment must be reported by the investigator. In addition, any SAEs which occur as a result of protocol specific diagnostic procedures or interventions also must be reported.

The SAE report should comprise a full written summary, detailing relevant aspects of the SAEs in question. The SAE summary also must include the investigator's assessment of expectedness and relatedness to specific protocol treatment (e.g. radiation or surgery). When applicable, information from relevant hospital case records and autopsy reports should be included. Initial and follow-up information, when it becomes available, should be faxed to the RTOG SAE Fax Line [contact] or e-mailed to [contact]. Each participating site must report the SAE to their regulatory authority. RTOG will report the SAE to the FDA.

SAEs brought to the attention of the investigator at any time after cessation of treatment and considered by the investigator to be related or possibly related to treatment also must be reported.

All SAEs must be reported to RTOG by facsimile to the RTOG SAE Fax Line [contact] or e-mailed to [contact] within 24 hours. RTOG will complete a preliminary review of the SAE details and may contact the site with suggested revisions.

6.9.2

Assessment of Causality and Expectedness

Every effort should be made by the investigator to explain each SAE and assess its expectedness and relationship, if any, to study treatment. Causality should be assessed using the following categories: no (not related), or yes (reasonable possibility).

The investigator may change his/her opinion of expectedness and/or causality in light of follow-up information, by amending the SAE Report Form.

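### Arm 1 has no scheduled adverse-event assessment before 4-6 weeks after surgery, while Arm 2 has one on the last treatment day, so non-serious perioperative events may be unequally ascertained

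*Combined protocol and SAP*

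**What the plan says.** The Appendix II row "Adverse event assessment" has four marks: Arm 1 at 4-6 weeks post-op, Arm 2 on the last SBRT day, Arm 2 at 4-6 weeks after SBRT, and the follow-up column shared by both arms. The three earlier Arm 1 columns (before surgery, during surgery, before discharge) carry no adverse-event mark.

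Toxicity is a between-arm comparison. Section 2.2.4 says that "specific comparisons will include adverse events at 1, 3, 12, 24, and 36 months post-therapy". Section 13.2.6 lists adverse-event frequency as a secondary endpoint, and Section 13.5.3 plans Fisher's exact test between arms without fixing a time point.

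The text also sets recording duties that do not depend on the calendar:

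- Section 6.9: "It is the responsibility of the investigator to document all adverse events which occur during the study".
- Section 6.8.1: adverse events "experienced by patients accrued to this protocol should be reported on the AE section of the appropriate case report form".
- Section 6.9.1: "Any SAE that occurs during any part of protocol treatment and 30 days after whether or not related to the study treatment must be reported". The seriousness criteria in Section 6.8.2 include death, life-threatening events and "Inpatient hospitalization or prolongation of existing hospitalization".

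Section 8.4, on adverse-event reporting for surgery, refers the reader only to Section 6.9. The case-report-form instruction in Section 6.8.1 sits under a heading about radiation therapy, and Section 8.4 does not cite it.

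**The concern.** Many surgical complications arise in hospital, in the days after the operation. That is the interval in which Arm 1 has no scheduled assessment, whereas Arm 2's treatment course closes with one. A graded assessment on a fixed date finds minor events that an unprompted duty to record can miss. If one arm is asked at the end of treatment and the other is not, part of any observed difference in toxicity may come from the schedule and not from the treatments.

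What is at stake is the secondary toxicity comparison. Section 13.3 expects a more favourable toxicity profile with SBRT, and this trial collects no quality-of-life data (Section 1.2.3). Adverse events are therefore its main evidence on tolerability.

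**Working it through.** The plan states no figure on this point, so there is nothing to reproduce. The check is a column count followed by a reading of which events the other rules already catch.

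**1. Is the asymmetry real, or an effect of the table extraction?** The row splits into 11 fields, the same number as the history-and-physical, performance-score and research-blood rows, and all four align with the header.

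| Calendar row | Arm 1 before discharge | Arm 1, 4-6 weeks | Arm 2 last SBRT day | Arm 2, 4-6 weeks |
|---|---|---|---|---|
| Adverse events | no | yes | yes | yes |
| Research blood | yes | yes | yes | yes |
| History and physical | no | yes | no | yes |

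Scheduled adverse-event assessments through the 4-6 week visit: Arm 1 = 1, Arm 2 = 2.

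**2. How long is the gap?** In Arm 1 the first scheduled assessment falls 4 × 7 = 28 to 6 × 7 = 42 days after surgery. In Arm 2 it falls on the last treatment day, with the course planned over 10-15 days and up to 20 permitted (Section 6.1.4). Section 1.4 gives surgical hospital stays of 1-3 weeks. If that stay is counted from the operation (an assumption), discharge falls at days 7 to 21. The first scheduled assessment then comes between 28 − 21 = 7 and 42 − 7 = 35 days after discharge.

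**3. Which perioperative events do the other rules catch?**

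- *Serious events:* caught in both arms during treatment and for 30 days after, whether or not related.
- *Non-serious events still present at 4-6 weeks:* caught by the scheduled visit in both arms.
- *Non-serious events that resolve before 4-6 weeks:* these rest on the general duty in Sections 6.8.1 and 6.9, with no scheduled prompt in Arm 1. The calendar does not say that the 4-6 week assessment looks back to the day of surgery. Section 8.3 lists events such as atelectasis and wound infection, which can be of this kind. A surgical patient is already an inpatient, so under the hospitalization criterion such an event becomes serious only if it prolongs the stay.

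**4. Do the data forms fill the gap?** Section 12.1 makes the surgical forms due within 4 weeks of surgery, and the follow-up form is due every 3 months in years 1-2. The contents of the forms are not in the documents, so it cannot be settled whether the surgical form collects graded complications.

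**5. Direction.** Missed events in Arm 1 lower its observed rate, and an extra prompt in Arm 2 can only raise Arm 2's. Both would make surgery look better relative to SBRT.

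**The case against.** The strongest reply is that the calendar is not the only route for adverse events. The duty in Section 6.9 is continuous and covers both arms. The definition in Section 6.8.1 extends to procedures, so it includes surgery. Because Section 6.9 opens with the duty to document all events, the pointer in Section 8.4 is not limited to serious ones. Section 8.1.6 asks for follow-up of surgical complications, in-hospital events leave a hospital record, and the 4-6 week visit can collect earlier events in retrospect. The comparisons named in Section 2.2.4 start at 1 month, close to a visit that both arms have, and no end-of-treatment contrast is specified. All of this stands, and it keeps the point small. It does not explain why one arm is prompted at the end of treatment and the other is not. The list in Section 2.2.4 is also not exclusive, and Section 13.5.3 sets no time limit.

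Three stronger readings are tempting, and the documents do not support them.

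- *That perioperative events are under-captured.* The calendar shows an unequal schedule, not a loss. Given the duties above, the most that follows is that ascertainment may be unequal.
- *That the loss can be sized from the plan's own complication rates.* Section 1.1.2 reports that "operative complications occurred in 27% of patients with screen-detected lung nodules who underwent a thoracotomy", and 0.27 × 38 is about 10 patients (76 / 2 = 38 per arm). The documents do not divide that 27% by seriousness, and the serious share is already covered. The same section gives 7.4% for grade 3 or higher complications after VATS lobectomy, or 0.074 × 38, about 3 patients. No document gives the fraction that would go unrecorded, so any total would be an assumption applied to the wrong base.
- *That the 15-point margin is undermined.* Section 13.3 rests the margin on equivalent survival through effective salvage. Toxicity is an additional expectation, and the example given is operative death, which the SAE rule captures.

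**Conclusion.** The schedule is unequal by arm in the perioperative window. The consequence is a possible, not demonstrated, inequality in how non-serious perioperative events that resolve before 4-6 weeks are ascertained. It would tend to understate Arm 1 toxicity and narrow any toxicity advantage of SBRT. It bears only on the secondary toxicity comparison; the primary endpoint, 2-year local-regional control, is unaffected. No numerical size can be given from the documents. The conclusion assumes that a scheduled assessment finds more minor events than an unprompted duty to record, and that the surgical form does not already collect graded complications. If that form does collect them, the gap is largely closed and only the calendar needs to say so. This is an inexpensive improvement, not a flaw that threatens the trial.

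**What to change.** - In Appendix II, mark the adverse-event assessment in the Arm 1 discharge column, so that each arm has one assessment as treatment closes and one at 4-6 weeks.
- State that the 4-6 week assessment covers all adverse events since the start of treatment, in both arms.
- Have Section 8.4 cite Section 6.8 as well as Section 6.9, so that the case-report-form instruction for non-serious events plainly applies to surgery.

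The cost is one further form entry per surgical patient, about 38 entries in all. It is made at discharge, a contact that occurs anyway, whether or not the patient consented to the research blood draw. Nothing changes in treatment, sample size or the primary analysis.
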